1.0 PROTOCOL/TRIAL SUMMARY

| Protocol Title | Phase I/II Study of Pembrolizumab and Cabozantinib for | | | | |
|------------------|---|--|--|--|--|
| Drotocol Number | | | | | |
| r rotocol Number | 10-2500 | | | | |
| Trial Phase | 1/11 | | | | |
| Objectives | To determine the efficacy based on objective response rate [ORR = complete response (CR) + partial response (PR)] of pembrolizumab and cabozantinib when administered in combination in subjects with locally advanced or metastatic renal cell carcinoma. | | | | |
| | Secondary Objectives: To characterize dose-limiting toxicities (DLTs), maximum tolerated dose (MTD), and recommended phase 2 dose (RP2D) for the combination. | | | | |
| | • To assess other measures of anti-tumor activity of the combination of pembrolizumab and cabozantinib in subjects with locally advanced or metastatic renal cell carcinoma. | | | | |
| | irRECIST (Immune-related response criteria) response Progression-free survival Overall survival Time to progression of overall disease Time to progression of bone metastasis or skeletal- related event Clinical benefit rate [complete response (CR) + partial response (PR) + stable disease (SD)] Duration of response or disease stability Duration on treatment in subjects treated beyond progression | | | | |
| | Exploratory Objectives, may include: Bone turnover markers, such as β C-terminal telopeptide (β-CTX), bone specific alkaline | | | | |

| | phosphatase and proceellagen type 1 amino terminal | | |
|--------------------|---|--|--|
| | propentide (P1NP). | | |
| | Bone scan responses | | |
| | • PD-L1 IHC testing on archival samples. | | |
| | • PD-L1 IHC testing on fresh tumor baseline and/or | | |
| | post-treatment samples. | | |
| | Evaluation of immuno-oncology markers | | |
| | | | |
| Endpoints | Primary Endpoint: | | |
| | To determine the efficacy (defined as objective response | | |
| | rate, ORR) of the combination of pembrolizumab and | | |
| | cabozantinib. | | |
| | Secondary Endpoints: | | |
| | To characterize dose limiting toxicities (DLTs), | | |
| | maximum tolerated dose (MTD), and recommended | | |
| | phase 2 dose (RP2D) for the combination of | | |
| | pembrolizumab and cabozantinib, as well as, other | | |
| | measures of efficacy including response by immune- | | |
| | survival overall survival time to progression of overall | | |
| | disease, time to progression of bone metastasis o | | |
| | skeletal-related events, clinical benefit rate [complete | | |
| | response (CR) + partial response (PR) + stable disease | | |
| | (SD)], duration of response or disease stability, and | | |
| | duration on treatment in subjects treated beyond | | |
| | progression. | | |
| | Exploratory Endpoint: | | |
| | We will include mandatory archival tumor collection and | | |
| | optional pre- and post-treatment tumor biopsies for PE | | |
| | L1 (QualTek Molecular Laboratories) and other immune- | | |
| | oncology testing which may include evaluation of other | | |
| ~ · · · · | immune checkpoint markers, immune cell markers, and | | |
| Subject Population | Clinical Indication: Renal Cell Carcinoma (RCC) | | |
| | Gender: Male and Female | | |
| | Age Range: 18-100 years | | |
| Trial Type | Interventional | | |

| Type of control | Non-randomized | | |
|---|--|--|--|
| Description of Study Agents | Pembrolizumab (Keytruda®) will be administered intravenously (IV). The manufacturer (Merck) is providing this product. | | |
| | 2. Cabozantinib (CABOMETYX [™]) will be administered orally. This is standard therapy for RCC. | | |
| Trial Blinding | Open-label | | |
| Treatment Groups | Single arm combination study | | |
| Number of trial subjects | 25-55 | | |
| Estimated enrollment period | 3 years | | |
| Estimated duration of trial | 5 years | | |
| Duration of Participation | 5 years | | |
| Estimated average length of treatment per subject | 8 months | | |

2.0 TRIAL DESIGN

2.1 Description of Study

This is a Phase I/II open-label study designed to evaluate the combination of pembrolizumab and cabozantinib in subjects with locally advanced, recurrent, or metastatic renal cell carcinoma.

Sequential dose escalation of cabozantinib with standard dose pembrolizumab will occur in the phase I dose escalation part of the study to determine the recommended phase 2 dose (RP2D). Subsequently, subjects will receive cabozantinib at the RP2D in combination with pembrolizumab in the phase II dose expansion part of the study. A standard 3+3 design will be used in Phase I to determine RP2D and a Simon two-stage design will be used in Phase II to determine efficacy of the combination. The planned enrollment for this study is approximately 25-55 total subjects, to account for screen failures, in order to achieve 6-9 evaluable subjects in Phase I dose escalation and 20-38 evaluable subjects in Phase II dose expansion.

Pembrolizumab will be administered by IV infusion on Day 1 of 21-day cycles. Cabozantinib will be taken orally once daily on a continuous basis. Subjects may continue treatment in the absence of unacceptable toxicity or clinically compelling disease progression. Treatment beyond progression per standard RECIST v1.1 criteria may be allowed if certain criteria are met and with the approval of the Principal Investigator.

2.1.1 Phase I Dose Escalation

Approximately 6-9 subjects will be enrolled using a standard 3+3 design. Three to six subjects will be enrolled in each dose cohort and receive cabozantinib and pembrolizumab in accordance with the dose escalation rules described below to determine the maximum tolerated dose (MTD) and RP2D (Section 2.1.3). The dose limiting toxicity (DLT) assessment window will be 21 days (Days 1–21 of Cycle 1). If a delayed DLT is observed, the DLT assessment window may be extended after the first administration of pembrolizumab and cabozantinib for all subjects in that cohort and any subsequent dose-escalation cohorts.

Any dose-escalation stage subject who does not complete the DLT assessment window for a reason other than a DLT will be considered non-evaluable for dose escalation decisions, as well as, the MTD assessment and may be replaced by an additional subject at that same dose level.

A subject who has any component of study treatment held during the DLT assessment window for a reason other than a DLT such that administration of the next planned pembrolizumab dose is delayed by more than 7 days and/or $\geq 25\%$ of the planned cabozantinib doses are missed, will be considered non-evaluable for dose-escalation decisions and the MTD assessment and may be replaced by an additional subject at that same dose level.

| Cohort | Pembrolizumab Dose | Cabozantinib Dose |
|--------|-------------------------|-------------------|
| -1 | 200 mg IV every 3 weeks | 20 mg PO daily |
| 1* | 200 mg IV every 3 weeks | 40 mg PO daily |
| 2 | 200 mg IV every 3 weeks | 60 mg PO daily |

* Starting dose level.

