2.1.3 Dose Escalation Rules

Pembrolizumab will be administered at a fixed dose of 200 mg IV every 21 days on Day 1 of each cycle.

The starting dose of cabozantinib for subjects in the first cohort will be 40 mg PO once daily for 21 consecutive days of each cycle (Days 1–21). For the second cohort, the dose of cabozantinib will be 60 mg PO once daily. If the starting dose of 40mg is not tolerated (2 or more out of 6 subjects experiencing DLT), then a lower dose of 20 mg will be evaluated.

Once the DLT assessment period has passed, pembrolizumab and/or cabozantinib may be held or dose modified independent of the other agent for adverse events attributed to one but not both drugs. The Principal Investigator should be notified when this occurs.

In addition to any DLTs, other available relevant demographic, adverse event, laboratory, and dose administration data will be reviewed prior to all dose-escalation decisions.

Dose escalation will occur in accordance with the rules:

- A minimum of 3 subjects will be enrolled in each cohort.
- If none of the first 3 DLT-evaluable subjects experiences a DLT, enrollment of the next cohort may proceed.
- If 1 of the first 3 DLT-evaluable subjects experiences a DLT, the cohort will be expanded to a minimum of 6 subjects. If there are no further DLTs in the first 6 DLT-evaluable subjects, enrollment of the next cohort may proceed.
- If 2 or more of the first 6 DLT-evaluable subjects in a cohort experience a DLT, the MTD will have been exceeded and dose escalation will stop. The preceding cohort will also be expanded to a minimum of 6 subjects, unless 6 subjects have already been evaluated at that dose level.
- If the MTD is exceeded at any dose level, the highest dose at which fewer than 2 of 6 DLTevaluable subjects experience a DLT will be declared the MTD.
- If the MTD is not exceeded at any dose level, the highest dose administered in this study will be declared the maximum administered dose.
- Any dose level may be expanded in the absence of a DLT if warranted based on investigator evaluation of non-DLT adverse events, including events occurring after Cycle 1 and events observed in the expansion cohorts.
- To be considered evaluable for dose escalation, subjects must have received at least 1 dose of pembrolizumab and ≥75% of planned dosing of cabozantinib prior to completing the DLT assessment window of 21 days.

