2.1.4 Definition of Maximum Tolerated Dose (MTD)

The Maximum Tolerated Dose (MTD) is defined as the highest dose level with no more than 1 DLT reported in 6 DLT-evaluable subjects.

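### The stated Phase I size of about 6-9 subjects does not match the plan's own escalation, MTD and RP2D rules: an RP2D needs at least 9, two full cohorts make 12, and 18 is possible but rare

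*Combined protocol and SAP*

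**What the plan says.** Section 2.1.1 gives the size: "Approximately 6-9 subjects will be enrolled using a standard 3+3 design". Section 2.1, repeated in 8.2.5, gives it as evaluable subjects: "in order to achieve 6-9 evaluable subjects in Phase I dose escalation and 20-38 evaluable subjects in Phase II dose expansion". The total is put at roughly 25-55, including screen failures.

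The rules that generate the size are these:

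- **Cohorts (2.1.1).** "Three to six subjects will be enrolled in each dose cohort". Three levels are listed: 40 mg (start), 60 mg and 20 mg.
- **Escalation (2.1.3).** "If none of the first 3 DLT-evaluable subjects experiences a DLT, enrollment of the next cohort may proceed". Also, "If 1 of the first 3 DLT-evaluable subjects experiences a DLT, the cohort will be expanded to a minimum of 6 subjects".
- **Failure of a higher dose (2.1.3).** With 2 or more DLTs in the first 6, escalation stops. "The preceding cohort will also be expanded to a minimum of 6 subjects", unless it already has 6. If 40 mg fails, 20 mg is evaluated.
- **No failure (2.1.3).** The highest dose given is declared the maximum administered dose. No minimum of 6 is attached.
- **MTD (2.1.4).** "the highest dose level with no more than 1 DLT reported in 6 DLT-evaluable subjects".
- **RP2D (2.1.5).** The 60 mg and 40 mg conditions are both expressed out of 6, and the RP2D is capped at the MTD.

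Sections 2.1.7 and 8.2.5 allow Phase I subjects treated at the RP2D to count in Stage I of Phase II.

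**The concern.** A 3+3 design has no fixed size, so a planning range should span what its rules usually produce. Here the top of the range equals the smallest size at which the plan's own RP2D definition can be met. Any ordinary complication, such as a single DLT among the first 3 at 40 mg followed by a full cohort at 60 mg, goes past it.

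The range also feeds the 25-55 total, which must cover screen failures. Because 6-9 is stated in evaluable subjects, replacements for non-evaluable subjects come on top. If Phase I runs to 12 or more, fewer places are left for screen failures and replacements, although the protocol has been followed exactly.

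**Working it through.** **1. Check on the plan's own DLT table.** Table 12 reproduces. At a rate of 0.20, P(0 of 3) = 0.8³ = 0.51, and P(0 or 1 of 6) = 0.8⁶ + 6 × 0.2 × 0.8⁵ = 0.262 + 0.393 = 0.66. All 12 cells agree to two decimals. The 6-9 range has no stated derivation. Arithmetically it is 3+3 to 3+6, and no reading of the rules limits Phase I to it.

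**2. Sizes that can occur (no rates needed).**

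| Size | Path |
|---|---|
| 6 | 0/3 at 40 mg, 0/3 at 60 mg: maximum administered dose, but no RP2D under 2.1.5 |
| 6 | 2 or more DLTs in the first 3 at 40 mg and again at 20 mg: no MTD |
| 9 | 3 at 40 mg + 6 at 60 mg; or 6 at 40 mg + 3 at 60 mg; or 3 at 40 mg + 6 at 20 mg |
| 12 | two cohorts of 6, e.g. 1/6 at 40 mg, then 6 at 60 mg |
| 18 | 0/3 at 40 mg; 60 mg fails after 6; 40 mg expanded to 6 and reaches 2 or more; 6 at 20 mg |

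Fifteen is also reachable.

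**3. How often more than 9.** The documents assume no true DLT rates, so the rates below are assumptions. A cohort is taken to stop at 3 once it has 2 or more DLTs. For each dose let a = P(0 of 3), b = P(1 of 3) and c = P(2 or more of 3). More than 9 subjects arise in three ways:

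- A: 0/3 at 40 mg, then 60 mg fails after 6, or fails in 3 and the expanded 40 mg cohort also fails: a40 × [F + c60 × c40]
- B: 1/6 at 40 mg, then 60 mg goes to 6: b40 × a40 × G
- C: 40 mg fails after 6 (1/3, then at least one more), then 20 mg goes to 6: b40 × (1 − a40) × (1 − c20)

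*Six required at the declared dose:* F = a60 × c60 + b60 × (1 − a60); G = 1 − c60.

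*0/3 at 60 mg is enough:* F = b60 × (1 − a60); G = b60. Six are still required at 40 or 20 mg once a higher dose has failed, because 2.1.3 then sets the MTD on 6.

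Worked for .05/.10/.20: a40 = .729, b40 = .243, c40 = .028; a60 = .512, b60 = .384, c60 = .104; c20 = .00725.

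- Six required: F = .0532 + .1874 = .2406. A = .729 × (.2406 + .0029) = .1776; B = .1771 × .896 = .1587; C = .0659 × .9928 = .0654. Sum = 0.40.
- 0/3 enough: A = .729 × (.1874 + .0029) = .1387; B = .1771 × .384 = .0680; C = .0654. Sum = 0.27.

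| Assumed rates 20/40/60 mg | P(>9), six required | P(>9), 0/3 at 60 mg enough | P(0/3 then 0/3) = a40 × a60 |
|---|---|---|---|
| .05/.10/.10 | 0.30 | 0.16 | 0.53 |
| .05/.10/.20 | 0.40 | 0.27 | 0.37 |
| .10/.20/.33 | 0.54 | 0.44 | 0.15 |
| .10/.20/.40 | 0.54 | 0.46 | 0.11 |

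With six required, full enumeration gives a mean size of 9.9-10.8 in these scenarios. P(18) is 0.2-2.2% here and stays below 3% at harsher rates. It reaches about 7% only if cohorts are always filled to 6 after two early DLTs.

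Sensitivity: if every rate were 1%, P(>9) falls to 0.03 with six required and to about 0.003 otherwise. If 0/3 were also accepted at 20 mg, against the MTD rule in 2.1.3, C becomes b40 × (1 − a40) × b20 and the four-scenario range is 0.10-0.32.

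**4. The total.** Stage II ends at 38 evaluable subjects.

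| Phase I size | No overlap | 6 RP2D subjects counted in Stage I |
|---|---|---|
| 9 | 9 + 38 = 47 | 47 − 6 = 41 |
| 12 | 12 + 38 = 50 | 50 − 6 = 44 |
| 18 | 18 + 38 = 56 | 56 − 6 = 50 |

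All figures are before screen failures and replacements. At the low end, 6 + 20 = 26 already exceeds 25, so the stated total seems to presuppose some overlap, but no amount is given.

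**The case against.** The strongest reply is that 6 is a legitimate outcome. Section 2.1.3 allows escalation after 0/3, orders expansion to 6 only after a DLT or when a higher dose fails, and closes a well-tolerated escalation with a maximum administered dose. A reader might infer that nine is an absolute floor, or that six can arise only when 40 mg and 20 mg both fail. The text does not support either: 0/3 plus 0/3 is a permitted ending, with probability 0.11-0.53 in the assumed scenarios. This stands, and it is why both readings are shown. It does not rescue the range, because 2.1.5 then names no RP2D, and the upper end fails on the looser reading too.

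Second, the size is hedged as approximate, and the cohort sizes and dose levels beside it show that larger numbers are possible. That is fair for a stray extra subject. It does not cover a range that misses on one side with probability 0.16-0.54.

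Third, the effect on the total is limited. A reader might infer that planned enrollment of 55 is likely to be breached. It is not: with 6 subjects overlapping, even the 18-subject path gives 50. Exceeding 55 before screen failures and replacements needs the rare 18-subject path, no overlap, and continuation to the second stage. This also stands.

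**Conclusion.** The point holds. The stated 6-9 is not what the plan's rules deliver, and its upper end is too low whichever reading of 2.1.3-2.1.5 applies. The reachable sizes (9 for an RP2D, 12 for two full cohorts, 18 at most) follow from the text alone. The probabilities rest on assumed DLT rates and on stopping a cohort at 3 after two DLTs; with very low toxicity, more than 9 would be unusual.

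Behind the size is an unresolved conflict: 2.1.4 and 2.1.5 need 6 subjects at the declared dose, while 2.1.3 lets escalation end with 3 at the top dose. The documents do not say which governs.

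Severity is minor. A reader might infer that the efficacy conclusions are affected. Nothing here changes the Simon boundaries, error rates or planned analyses. The consequence is a planning figure that is wrong as written and a smaller margin within the enrollment total.

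**What to change.** 1. Reconcile the 6-subject definitions in 2.1.4 and 2.1.5 with the maximum-administered-dose rule in 2.1.3. Which of them governs is for the sponsor to decide; this review does not choose.
2. Restate the Phase I size in 2.1, 2.1.1 and 8.2.5 to match: 9-12 DLT-evaluable subjects (maximum 18) if 6 are required at the RP2D, or 6-12 (maximum 18) if they are not.
3. Re-derive the 25-55 total from that figure, stating the assumed overlap between Phase I and Stage I and the allowance for screen failures and non-evaluable subjects.

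The cost is one clarifying sentence and a few restated figures in an amendment. No additional data are needed, and the Phase II design is unchanged. The clarification does settle an ambiguity in the escalation rules, so it should be made explicitly and not left to the restated number.

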2.1.2 Definition of Dose Limiting Toxicity

Any one of the following events will be considered a DLT if it occurs during the DLT assessment window **and** is assessed by the investigator to be **likely related** to study treatment (pembrolizumab and/or cabozantinib).

- Grade \geq 3 non-hematologic, non-hepatic adverse event, with the following exceptions:
 - Grade 3 hypertension that resolves to Grade ≤ 2 with addition or adjustment of antihypertensive therapy in ≤ 7 days
 - Grade 3 fatigue that resolves to Grade ≤ 2 in ≤ 5 days
 - Grade 3 laboratory abnormalities that are asymptomatic, considered by the investigator not to be clinically significant, and that resolve to Grade ≤ 2 in ≤ 48 hours
 - Grade 3 rash that resolves to Grade ≤ 2 in ≤ 5 days with or without therapy equivalent to prednisone 10 mg/day or less
 - Grade 3 hand-foot syndrome that resolves to baseline within 3 weeks
 - Grade 3 arthralgia and/or myalgia that resolves to baseline within 3 weeks
 - Grade 3 autoimmune thyroiditis or other endocrine abnormality that resolves to Grade ≤ 2 within 3 weeks
- Grade 3 nausea, vomiting, or diarrhea lasting >72 hours despite maximal medical therapy.
- Grade \geq 4 neutropenia (ANC < 500 cells/ μ L) lasting > 7 days
- Grade \geq 3 febrile neutropenia
- \circ Grade \geq 4 anemia
- o Grade ≥ 4 thrombocytopenia, or Grade 3 thrombocytopenia associated with clinically significant bleeding
- Grade \geq 3 elevation of serum hepatic transaminase (ALT or AST).
- Grade \geq 3 elevation of serum total bilirubin.
- ALT or AST > 3 × upper limit of normal (ULN) **AND** total bilirubin >2 × ULN will require permanent treatment discontinuation.

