6.0 TRIAL SCHEDULE OF EVENTS CHART

| Trial Period: | Trial Period: Screening Treatment Cycles ^a | | | | | | | End of Treatment/ Follow Up Visit | Survival Follow-Up ^m | |
|--|---|----|---------|---------|---------|----------|-----------------------|--------------------------------------|---|------------------|
| | Main Study | | | | | Te be | o be repe yond 7 c | ated ycles | Safety Follow-up | Overall Survival |
| Treatment Cycle/Title: | Screening | 1 | 2 | 3 | 4 | 5 | 6 | 7 | | Every 6 months |
| Scheduling Window (Days): | -28 to -1 | | ± 3 | ± 3 | ± 3 | ± 3 | ± 3 | ± 3 | Within 30 days post treatment discontinuation | ± 1 month |
| Informed Consent | Х | | | | | | | | | |
| Inclusion/Exclusion Criteria | Х | | | | | | | | | |
| Demographics and Medical History | Х | | | | | | | | | |
| Prior and Concomitant Medication Review | Х | Х | Х | Х | Х | Х | Х | Х | Х | |
| Pembrolizumab Treatment Administration ¹ | | Х | Х | Х | Х | Х | Х | Х | | |
| Cabozantinib Treatment Administration | | Х | Х | Х | Х | Х | Х | Х | | |
| Post-study Anticancer Therapy Status | | | | | | | | | Х | |
| Survival Status ^m | | | | | | | | | Х | X ^m |
| Review Adverse Events | Х | Х | Х | Х | Х | Х | Х | Х | Х | |
| Full Physical Examination | Х | Х | Х | Х | Х | Х | Х | Х | Х | |
| Vital Signs and Weight | Х | Х | Х | Х | Х | Х | Х | Х | Х | |
| Height | Х | | | | | | | | | |
| ECOG Performance Status | Х | Х | Х | Х | Х | Х | Х | Х | Х | |
| 12-lead EKG | Х | | | | Х | | | X ^k | Х | |
| Pregnancy Test – Urine ^b | Х | Xj | Х | Х | Х | Х | Х | Х | | |
| PT/INR, aPTT, LDH | Х | | | | | | | | | |
| CBC with Differential | Х | Xj | Х | Х | Х | Х | Х | Х | Х | |
| Comprehensive Serum Chemistry Panel, including Phosphorus | Х | Xj | Х | Х | Х | Х | Х | Х | X | |
| Urinalysis | Х | Xj | Х | Х | Х | Х | Х | Х | Х | |
| Total T3, Free T4, and TSH ⁱ | Х | | | | Х | | | Х | Х | |

| Trial Period: | Screening | Treatment Cycles ^a | | | | | End of Treatment/ Follow Up Visit | Survival Follow-Up ^m | | |
|---|----------------------------|-------------------------------|-----|-----|-----|-----------------------------------|--------------------------------------|------------------------------------|---|-----------------|
| | Main Study Screening | | | | | To be repeated beyond 7 cycles | | ed cles | Safety Follow-up | Overall Surviva |
| Treatment Cycle/Title: | (Visit 2) | 1 | 2 | 3 | 4 | 5 | 6 | 7 | | Every 6 months |

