| Scheduling Window (Days): | -28 to -1 | | ± 3 | ± 3 | ± 3 | ± 3 | ± 3 | ± 3 | Within 30 days post treatment discontinuation | ±1 month |
| Tumor Imaging ^e (CT or MRI C/A/P +/- Whole Body Bone Scan ^d) | х | | | | X | | | х | | |
| RECIST 1.1 and irRECIST radiology read ^c | Х | | | | Х | | | Х | | |
| Archival Tumor Collection | Х | | | | | | | | | |
| Optional Fresh Tumor Biopsies (baseline and post-treatment) | Xe | | Xe | | | | | | | |
| • PD-L1 Testing | Х | | Х | | | | | | | |
| Immuno-Oncology Marker Testing | X | | X | | | | | | | |
| Correlative Studies | | | | | | | | | | |
| Bone Turnover Markers^g (in subjects with bone metastases only) | | Х | Х | | Х | | | X† | | |

^a Each treatment cycle = 3 weeks.

^b Urine pregnancy test is required only in women of childbearing potential.

^c CT or MRI CAP +/- bone scan and RECIST 1.1 assessments will be obtained at baseline and after every 3 cycles. irRECIST = immune-related response criteria. PET/CT is an acceptable alternative imaging modality. All scans can be performed \pm 7 days from the scheduled date.

d Whole Body Bone Scan is required for subjects with known or suspected bone metastases. All scans can be performed \pm 7 days from the scheduled date.

^e The baseline optional fresh tumor biopsy should be obtained during the screening period, prior to C1D1 treatment. The post-treatment optional fresh tumor biopsy should be obtained approximately 3-6 weeks (during cycle 2). Subjects may consent for separately for either baseline and/or post-treatment biopsies.

g Bone turnover markers may include β C-terminal telopeptide (β-CTX), bone specific alkaline phosphatase, and procollagen type 1 amino-terminal propeptide (P1NP). †Bone turnover markers will be collected through cycle 7 but not beyond. Bone tumor markers are not required during the second course of treatment.

ⁱ Total T3 = Total thriiodothyronine, Free T4= T4 (thyroxine) Free

^j Screening labs and pregnancy tests do not need to be repeated at C1D1 if done within 7 days of C1D1.

^k EKG tests will be performed through cycle 7, and then only as clinically indicated.

¹ In the absence of disease progression, pembrolizumab may be administered for up to 35 cycles (first course). If the patient progresses after discontinuing pembrolizumab, they may resume dosing for up to 17 additional cycles (second course), providing they meet criteria for retreatment. See protocol section 5.2.1 for additional information.

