7.1.3 Laboratory Procedures/Assessments

Details regarding specific laboratory procedures/assessments to be performed in this trial are provided below Laboratory Safety Evaluations (Hematology, Chemistry and Urinalysis)

Laboratory tests for hematology, chemistry, urinalysis, and others are specified in Table 10.

Table 10: Laboratory Tests

| Hematology | Chemistry | Urinalysis | Other |
|----------------------------------|---|--|--|
| Hematocrit | Albumin | Blood | Serum β -human chorionic gonadotropin (β -hCG) ² |
| Hemoglobin | Alkaline phosphatase | Glucose | |
| Platelet count | Alanine aminotransferase (ALT) | Protein | PT (INR) |
| WBC (total and differential) | Aspartate aminotransferase (AST) | Specific gravity | aPTT |
| Red Blood Cell Count | Carbon Dioxide | Microscopic exam (If abnormal results are noted) | Total triiodothyronine (T3) |
| Absolute Neutrophil Count | Lactate dehydrogenase (LDH) ¹ | | Free thyroxine (T4) |
| Absolute Lymphocyte Count | Calcium | Urine pregnancy test ² | Thyroid stimulating hormone (TSH) |
| | Chloride | | |
| | Glucose | | |
| | Phosphorus | | |
| | Potassium | | |
| | Sodium | | |
| | Total Bilirubin | | |
| | Direct Bilirubin (If total bilirubin is elevated above the upper limit of normal) | | |
| | Total protein | | |
| | Blood Urea Nitrogen | | |
| 1 LDH only required at screening | • | • | • |

2 Perform on women of childbearing potential only. If urine pregnancy results cannot be confirmed as negative, a serum pregnancy test will be required.

After Cycle 1, pre-dose laboratory procedures can be conducted up to 72 hours prior to dosing. Results must be reviewed by the investigator or qualified designee and found to be acceptable prior to each dose of trial treatment.

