7.1.5.2 Treatment Period

All visits must occur within ± 3 days from the scheduled date, unless otherwise noted. All assessments will be performed on the day of the specified visit unless a time window is specified. Assessments scheduled on the day of study treatment administration (Day 1) of each cycle should be performed prior to study drug infusion, unless otherwise noted. C1D1 laboratory assessments do not need to be repeated if screening labs were done within 7 days of C1D1.

See the study Schedule of Events (Section 6.0) for schedule of treatment period assessments.

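### Laboratory and serial-measurement DLTs are not reliably ascertained: the only scheduled on-treatment check falls nominally on Day 22, one day after the DLT window closes

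*Combined protocol and SAP*

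**What the plan says.** **Window.** Section 2.1.1: "The dose limiting toxicity (DLT) assessment window will be 21 days (Days 1–21 of Cycle 1". Section 2.1.2: "Any one of the following events will be considered a DLT if it occurs during the DLT assessment window". Section 2.1.1 also allows a later change: "If a delayed DLT is observed, the DLT assessment window may be extended after the first administration of pembrolizumab and cabozantinib". That step is optional and depends on a delayed DLT having already been seen.

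**Criteria.** Section 2.1.2 includes three kinds of event that depend on laboratory tests or measurements:
- By grade alone: Grade ≥3 ALT/AST, Grade ≥3 bilirubin, Grade ≥4 anemia, Grade ≥4 thrombocytopenia.
- By grade and minimum duration: ANC <500 for more than 7 days.
- Exceptions that depend on recovery: asymptomatic Grade 3 laboratory abnormalities resolving within 48 hours, and Grade 3 hypertension resolving within 7 days.

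**Schedule.** The Section 6.0 chart has one column per cycle ("Each treatment cycle = 3 weeks"), no mid-cycle visit and no separate chart for dose-escalation subjects. Blood counts, chemistry, vital signs and adverse-event review are each marked once per cycle. Section 7.1.5.2: "Assessments scheduled on the day of study treatment administration (Day 1) of each cycle should be performed prior to study drug infusion". Section 7.1.2.3 ties vital signs to each dose. Footnote j adds: "Screening labs and pregnancy tests do not need to be repeated at C1D1 if done within 7 days of C1D1".

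**Timing allowances.** Sections 5.2.2 and 7.1.5.2 let Day 1 move by ±3 days. Section 7.1.3: "After Cycle 1, pre-dose laboratory procedures can be conducted up to 72 hours prior to dosing".

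**The concern.** The Cycle 1 Day 1 assessments precede the first infusion, so they cannot show a toxicity of treatment. The first required on-treatment laboratory set is the one taken before the Cycle 2 dose. In the nominal schedule that is one day after the window closes. Followed literally, the rule can exclude the only on-treatment sample that the schedule requires.

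Two problems follow. First, whether a given laboratory finding counts as a DLT depends on an administrative choice of sampling day. Second, an abnormality without symptoms that arises and recovers between the two visits need never be seen, and one late sample cannot show how long an abnormality lasted.

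DLTs, MTD and RP2D are secondary endpoints. The RP2D rule in Section 2.1.5 is a count: fewer than 2 of 6 subjects with a DLT at 60 mg makes 60 mg the RP2D, and that dose goes into Phase II. With 6–9 Phase I subjects, one uncounted DLT can change the outcome of the rule.

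**Working it through.** **1. When the first on-treatment sample is due.** Cycles last 21 days, so nominal Cycle 2 Day 1 is Day 22. With ±3 days, the visit falls on Days 19–25. Laboratory tests may precede dosing by 72 hours:
- nominal visit: sample on Days 19–22;
- earliest visit (Day 19): sample from Day 16;
- latest visit: sample as late as Day 25.

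A sample on Day 21 or earlier is in the window; one on Days 22–25 is not. Both comply with the protocol.

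**2. What one sample can show (illustration).** Assume onset is uniform over the 20 days from Day 2 to Day 21, the abnormality lasts d days, and there is one sample on Day L. It is present at sampling if onset ≤ L < onset + d.

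| Duration | Day 19 | Day 22 | Day 25 |
|---|---|---|---|
| 8 days | 8/20 = 40% | 7/20 = 35% | 4/20 = 20% |
| 2 days | 2/20 = 10% | 1/20 = 5% | 0/20 = 0% |

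Even when the abnormality is present, one sample does not establish that it lasted more than 7 days or resolved within 48 hours.

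**3. Reproducing Table 12 (Section 8.2.5).** P(0 of 3) = (1−p)³. P(fewer than 2 of 6) = (1−p)⁶ + 6p(1−p)⁵. For p = 0.10, 0.20, 0.33, 0.40, 0.50, 0.60:
- 0 of 3: 0.729, 0.512, 0.301, 0.216, 0.125, 0.064;
- fewer than 2 of 6: 0.886, 0.655, 0.358, 0.233, 0.109, 0.041.

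All 12 entries agree with the table after rounding. The table treats every DLT as detected.

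**4. Effect of missed DLTs.** Let s be the share of true DLTs that is detected, independently between subjects, and replace p by q = p × s. The documents give no value of s, so a range is shown.

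| s | q at p = 0.33 | P(fewer than 2 of 6) | P(0 of 3) |
|---|---|---|---|
| 1 (Table 12) | 0.330 | 0.36 | 0.30 |
| 0.90 | 0.297 | 0.43 | 0.35 |
| 0.75 | 0.2475 | 0.54 | 0.43 |
| 0.50 | 0.165 | 0.74 | 0.58 |

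Example, s = 0.75: 0.7525⁶ + 6(0.2475)(0.7525⁵) = 0.182 + 0.358 = 0.540. At p = 0.40, P(fewer than 2 of 6) goes from 0.23 to 0.30, 0.42 and 0.66.

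**5. Direction.** Silent transient abnormalities and undocumented prolonged neutropenia are lost from the count. The 48-hour and 7-day clauses work differently: they are exceptions to a default DLT, so once the event has been found, failure to document recovery leaves it a DLT on a strict reading. The net direction is mainly, but not only, toward undercounting.

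**The case against.** A reader might infer that laboratory or duration-based DLTs cannot be ascertained at all. The documents do not support that, for these reasons:
- The Cycle 2 sample may be drawn inside the window.
- The hepatic, anemia and Grade ≥4 thrombocytopenia criteria have no duration element, so one positive sample is enough, and an abnormality that persists to the Cycle 2 sample would be found.
- Durations of symptoms such as nausea, diarrhea, fatigue or rash can be taken from the adverse-event start and stop dates required in Table 11.
- Sections 7.1 and 7.1.2.1 allow unscheduled assessments. Section 5.4.2 calls for more frequent monitoring once ALT, AST or bilirubin is raised, and Table 3 suggests considering weekly liver tests. These help to establish duration after a first abnormal result.

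A reader might also infer that a Day 22 finding can never be a DLT. Section 2.1.2 turns on when the event occurs, not when it is sampled, and Section 2.1.1 permits the window to be extended.

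Nor does a missed DLT necessarily fix the dose. Section 2.1.3 requires review of other available safety data before each escalation and lets a dose level be expanded without a DLT. Section 2.1.5 lets the RP2D be amended during Phase II.

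All of this stands and limits the claim. It does not close the gap. The extra assessments are discretionary, and a silent abnormality prompts no test. The blood-count instruction in Section 5.4.2 gives no interval. Extension requires that a delayed DLT be observed first. With no earlier sample, the onset of an abnormality found on Day 22 cannot be dated. A review of available data cannot use results that were never collected.

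Finally, the text is dated June 2021 and provides for subjects already past 35 cycles at the October 2020 version, so dose escalation is probably finished. That is an inference. It weakens the case for new Cycle 1 procedures but not for stating how collected Cycle 2 Day 1 findings are counted.

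**Conclusion.** The point holds as a problem of reliability. The DLT window and the schedule do not meet: the one required on-treatment sample may be in or out of the window, and the clauses on ANC duration, 48-hour laboratory recovery and 7-day blood-pressure recovery need serial measurements that the schedule does not require. Table 12 is correct as arithmetic but describes the design only under complete detection.

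At a true DLT rate of 0.33, the chance of fewer than 2 DLTs in 6 would be 0.43, 0.54 or 0.74 instead of 0.36 if 10%, 25% or 50% of DLTs were missed. Those shares are assumptions, as is independence between subjects. The figures show sensitivity; they do not estimate what happened in this trial. The documents do not show that any DLT was missed or that the selected RP2D was wrong.

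**What to change.** 1. State in Section 2.1.1 that the DLT window closes with the pre-dose Cycle 2 Day 1 assessment, so that qualifying findings at that assessment count as in-window. Bring Section 2.1.2 and the 21-day reference in the last rule of Section 2.1.3 into line. Word it so that an early Cycle 2 visit does not shorten the window.
2. Apply the same definition to the Cycle 2 Day 1 data already collected when preparing the DLT listing in Section 8.2.2.
3. Reconcile the duration-based clauses of Section 2.1.2 with the once-per-cycle schedule in Section 6.0. How to do so, including any visit timing or classification rule, is for the sponsor to decide; none is proposed here.

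Changes 1 and 2 need about one sentence, matching edits and a check of existing data, with no new visit. They do not recover abnormalities that came and went between visits, which is why change 3 is also needed. The downside is that slightly more DLTs may be counted, making escalation more conservative.
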